We undertook a scoping review to inform our proposal and choice of primary outcome measures (DAMA, emergency readmission), searching MEDLINE and EMBASE (via Ovid) on 31/09/2020. We used search terms relating to three domains: OST; health care facility; and outcomes ["delay\* OR readmission\* OR discharge], excluding sources reporting on neonates [NOT neonat\*]. We searched from 1/01/2000 and only reviewed sources presenting empirical data. This resulted in less than 250 unique sources. Timely OST provision for hospital inpatients and at emergency and acute admissions was evidenced to reduce rates of self-discharge and emergency readmission [5, 6, 36, 40, 44-46]. Qualitative data highlighted how the distress of opioid withdrawal could result in self-discharge [2, 8, 9, 30] with case reports cautioning of "the potential morbidity of methadone treatment interruption in the hospital setting" [47]. This evidence strongly suggests that interventions to improve OST provision in hospitals will have an important impact on reducing DAMA.

Systematic review data indicate that 25-30% of PWUO leave hospital prior to completing medical treatment [40]. Patients who leave hospital prematurely are 12 times more likely to be readmitted with a related diagnosis within 14 days, and twice as likely to die [40, 48, 49]. This exacerbates health inequalities among a marginalised population, increases health care system burden and contributes to escalating economic costs [32, 33, 50]. Economic analysis show that the average costs associated with a readmission within 30-days of DAMA are estimated as 56% higher than the costs associated with completing the initial hospitalization [33].

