### OUTCOME MEASURES

- Primary:
1. Discharge against medical advice (DAMA)
  2. Emergency hospital readmission within 28 days of discharge.
- Secondary:
3. Reported inpatient illicit drug use
  4. Time between admission, prescription of OST and receipt of OST.
  5. OST dose
  6. Provider knowledge and attitudinal change.

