**2. Controlled analysis using HES (difference-in-difference [10]).** This analysis will involve measuring the change in primary outcomes at iHOST sites before and after iHOST implementation and comparing this change to other hospitals over the same time period. HES does not show whether patients received OST in hospital, and we will therefore need to identify a group of patients who may benefit from iHOST. Our planned inclusion criteria will be all admissions at acute hospital trusts in the 12 months before or after the iHOST “go-live” date, the patient is aged 18-64 at admission, and the patient has an ICD-10 diagnosis of opioid dependence (F11) in any diagnostic position, either in that admission or an admission at any hospital nationally in the previous 12 months. For each admission we will derive the two primary outcomes: DAMA and 28-day emergency readmission. We have previously used HES to measure these outcomes in comparable populations [32, 76] and are familiar with the structure of HES. We will then fit logistic regression models where the dependent variable is the outcome and the independent variables include an interaction term between the iHOST site status and whether the patient was admitted before or after iHOST implementation. We will also include patient-level confounding variables such as age, comorbidities, and the primary reason for admission, and a random intercept for the hospital site. This analysis addresses the question “did the risk of self-discharge/readmission reduce more at iHOST sites than at other hospitals”? Depending on the number of patients with admissions at the same hospital both before and after iHOST “go-live”, or at similar dates at iHOST sites and other hospitals, it may also be possible to conduct a sub-analysis of within-patient differences using conditional regression.

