-serving a population of around 700,000 in Staffordshire, as well as providing specialist services to patients from beyond the region. ([Staffordshire Evidence Base: Population Demographics and Adult Social Care Needs February 2019](#)) Staffordshire Treatment and Recovery Service (STARS) is the community drug treatment provider for Staffordshire, which is operated by Humankind.

LEEDS: is the fourth most populous urban area in England. For 2019/2020 the number of adults on treatment for opiate use in Leeds was 2705 (NDTMS). St James's University Hospital is Europe's largest teaching hospital, providing local and specialist services for its immediate population of 770,000 and regional specialist care for up to 5.4 million people. In 2019/20 the hospital in-reach (liaison) team reviewed 1044 individuals. The local drug treatment provider is Forward Leeds, operated by Humankind and delivered in partnership with Leeds and Yorkshire Partnership NHS Foundation Trust.

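### The optional within-patient comparison of close-in-time admissions at iHOST and other hospitals is open to selection on the readmission outcome, so its odds ratio can partly reflect which hospital came first

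*Protocol*

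**What the plan says.** The passage is in the Protocol, Analysis, Quantitative evaluation, item 2 (controlled analysis using HES).

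- **Eligible admissions:** "Our planned inclusion criteria will be all admissions at acute hospital trusts in the 12 months before or after the iHOST" go-live date. The text does not restrict these to emergency admissions or to one admission per patient.
- **Outcomes:** "For each admission we will derive the two primary outcomes: DAMA and 28-day emergency readmission". Outcome measures, in section 5, defines the second of these as "Emergency hospital readmission within 28 days of discharge". Neither place says whether the readmission must be to the same hospital.
- **Main model:** logistic regression with an interaction between site status and period, patient-level confounders and a random intercept for hospital.
- **Optional addition:** a "sub-analysis of within-patient differences using conditional regression". It has two routes. The first begins "Depending on the number of patients with admissions at the same hospital both before and after iHOST" go-live. The second is "or at similar dates at iHOST sites and other hospitals, it may also be possible to conduct a sub-analysis of within-patient differences".

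The number of eligible patients is the only condition given for running the sub-analysis. The text gives no width for the date window and no rule for an admission that is itself the readmission. It does not say whether the sub-analysis keeps the site-by-period interaction.

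**The concern.** To enter by the second route, a patient must have a second admission close in time to the first. An emergency admission soon after discharge is also one of the two primary outcomes. For example, a patient is discharged from another hospital on 1 March and admitted as an emergency to an iHOST site on 10 March. If readmission to any hospital counts, the first admission is scored as readmitted because the second exists. The second is scored as readmitted only if a third follows.

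The dependence lies between the patient's own two rows, so conditioning on the patient cannot remove it. A plain iHOST-versus-other odds ratio would then carry a first-versus-second contrast. It could support or contradict the main result for reasons unrelated to iHOST, in an analysis that looks well controlled.

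**Working it through.** The protocol gives no figure for this sub-analysis, so there is none to reproduce.

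**1. Formula.** For 1:1 pairs the conditional odds ratio is the ratio of the two discordant counts. Let q be the share of pairs with iHOST first, a the probability that the earlier row is positive, and b the probability that the later row is positive, with rows independent and no iHOST effect. Then

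OR (iHOST v other) = [q·a(1−b) + (1−q)·(1−a)b] / [q·(1−a)b + (1−q)·a(1−b)].

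At q = 0.5 this is 1 whatever a and b are.

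**2. Limiting case.** If the pair lies within 28 days of discharge, the later admission is an emergency and readmission to any hospital counts, then a = 1 and OR = q/(1−q).

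- iHOST second in 60% of pairs: 0.4/0.6 = 0.67.
- iHOST second in 70%: 0.3/0.7 = 0.43.
- iHOST second in 35%: 0.65/0.35 = 1.86.

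**3. Wider windows.** Assumptions, none from the document: b = 0.25, a 25% risk in earlier rows not fixed by the pairing, all second admissions emergencies, and gaps uniform on 0 to W days.

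- W = 60: a = 28/60 + (32/60)(0.25) = 0.60, so a(1−b) = 0.45 and (1−a)b = 0.10. At q = 0.4, OR = 0.24/0.31 = 0.77. At q = 0.3, OR = 0.205/0.345 = 0.59.
- W = 90: a = 28/90 + (62/90)(0.25) = 0.483, so a(1−b) = 0.3625 and (1−a)b = 0.129. At q = 0.4, OR = 0.83. At q = 0.3, OR = 0.68.

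**4. Simulation under a different model, no iHOST effect.** Assumptions, again not from the document: gamma frailty, about 3 admissions a year, mean stay about 5 days, 85% emergencies, a 30% chance of switching hospital type between admissions, and the first qualifying consecutive pair per patient. With readmission to any hospital counted:

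| Window (days) | Readmitted, earlier v later | OR, mostly other-first | OR, balanced | OR, mostly iHOST-first |
|---|---|---|---|---|
| 28 | 87% v 33% | 0.53 | 1.03 | 1.84 |
| 60 | 52% v 30% | 0.68 | 1.00 | 1.48 |
| 90 | 42% v 29% | 0.73 | 1.00 | 1.34 |
| 180 | 34% v 28% | 0.85 | 1.01 | 1.16 |

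The iHOST-first share in the outer columns was 33% and 66% at 28 days and 21% and 79% at 180 days. The shrinkage is therefore not due to a milder order mix.

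**5. Same-hospital readmission only.** The paired admission can no longer be the outcome, and the earlier row is rarely positive: 4% v 23% at 28 days. The OR runs the other way, from 1.65 (mostly other-first) to 0.63 (mostly iHOST-first). In these runs it widened with the window, to 2.97 and 0.34 at 180 days.

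**6. DAMA.** The pairing does not set DAMA. It can enrich the earlier row if leaving early raises the chance of readmission. With an assumed 25% baseline and a readmission ratio R, the DAMA share in an earlier row selected for readmission is 0.25R/(0.25R + 0.75).

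- R = 2 (an assumption): 0.5/1.25 = 40%. OR = 0.21/0.24 = 0.88 at q = 0.4, and 0.195/0.255 = 0.76 at q = 0.3.
- R = 12: 3/3.75 = 80%. OR = 0.27/0.38 = 0.71 at q = 0.4, and 0.215/0.435 = 0.49 at q = 0.3. This is an outer illustration only. The Background figure, "Patients who leave hospital prematurely are 12 times more likely to be readmitted with a related diagnosis within 14 days", concerns a narrower outcome than 28-day emergency readmission for any cause.

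**The case against.** **Nothing is fixed by construction.** A reader might infer that the earlier admission is always scored as readmitted. That needs all three conditions in step 2, and the protocol sets none of them for the pairing. This objection stands. The text supports exposure to the bias, not a bias of known size or sign.

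**The order of hospitals is unknown.** A reader might infer that the sub-analysis would favour iHOST, because the Leeds site is described as "providing local and specialist services for its immediate population of 770,000 and regional specialist care for up to 5.4 million people" and the Stoke site also takes patients from beyond its region. That text says nothing about the order of admissions. Specialist referrals may be elective or transfers, in which case the later admission is not an emergency readmission. This stands too. Equally, nothing in the design balances the order.

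**The interaction may cancel it.** The section's main estimand is a site-by-period interaction. If cross-hospital pairs from both periods were analysed that way, an order effect stable over time would largely cancel under no effect. This is a fair point, but the protocol does not say that the sub-analysis uses that model. With a true effect, the share of iHOST-first pairs could itself change after go-live.

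**It is tentative, and detail belongs in the SAP.** The wording is conditional, a HES feasibility run at UCLH comes first, and refinement of the analysis plan is scheduled in Phases 1 and 2. The window and the readmission definition are ordinary SAP content, and their absence is no finding. What remains is that the protocol itself states a pairing rule that creates the dependence, with patient numbers as the only condition for using it.

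**Conclusion.** The concern holds in limited form. The cross-hospital route is open to selection on the readmission outcome, and a plain iHOST-versus-other conditional odds ratio from it would partly reflect which hospital came first. With readmission to any hospital counted, the distortion is complete only in the 28-day emergency case and partial with wider windows. It reverses if only same-hospital readmission counts, and it is close to nil at balanced order under no effect. The odds ratios above rest on assumed order shares, risks and windows, and show what could happen rather than what would. DAMA may be enriched in the earlier row but is not fixed by the pairing.

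A reader might also infer that the study's main comparison is compromised. It is not: the difference-in-difference model does not select patients on having a second admission. Severity is minor.

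**What to change.** In item 2 of the Quantitative evaluation, delete the cross-hospital alternative (the start of "or at similar dates at iHOST sites and other hospitals, it may also be possible to conduct a sub-analysis of within-patient differences", from 'or' to 'hospitals'). Keep the same-hospital before/after within-patient analysis and state that it uses the site-by-period interaction. In that route the before admission comes first at every hospital, so a stable order effect is shared with the comparator hospitals. Only pairs falling close to go-live can be each other's readmission.

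Do not substitute a rule that admits only cross-hospital pairs more than 28 days apart. If the pair are consecutive admissions, the earlier row then has no admission within 28 days and is pushed towards not readmitted. In that limit the OR becomes (1−q)/q, for example 0.6/0.4 = 1.5 where iHOST is second in 60% of pairs. Limiting the route to DAMA would lessen the problem but not remove it.

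The cost is one clause of text and the loss of one exploratory sub-analysis.

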## QUALITATIVE EVALUATION

Qualitative data generation will be informed by a topic guide informed by our review of the literature and Phase 1 PPI. We will explore with PWUO their experiences and perceptions of health issues, the barriers and facilitators to care seeking, and retention in hospital care. We will orientate toward understanding iHOST acceptability in its local context, but also how this might be improved, and extended (for example, in relation to hospital discharge planning; improvements in community OST treatment and access to primary care). We will undertake non-participant observations, using an observational tool informed by CFIR constructs [75] and through narrative field notes, to understand the local contexts, quality of iHOST implementation, and

contribution of each component toward change (including those unanticipated). With interviews, observations will help build a picture of how the hospital environment, including dynamics of staff-patient interaction and local policies (such as 'conduct contracts') impact the experience and feelings of 'safety' among PWUO, also to understand how/ in what way these are amenable to change.

All interviews and focus groups will be recorded (with the consent of participants) and transcribed verbatim. Interview field-notes and analytical memos will be generated throughout and integrated alongside transcripts in analyses. The PI is an experienced qualitative researcher and will lead analysis. Her approach is informed by constructivist grounded theory principles [77], with analysis beginning alongside and informing ongoing data generation. Initial coding will be inductive, comprising 'open' codes. This will inform the development of a coding framework, and subsequent second level coding and theory development. Preliminary analysis of qualitative datasets will also be conducted in collaboration with PPI working groups, with a focus on co-producing a cultural theory framework grounded in participant data, with meaningful explanatory value for both PWUO and health care providers. This will be iteratively developed, with initial concepts tested through further fieldwork and refined in discussion with multiple stakeholders (see synthesis below).

Our qualitative data will be analysed through triangulation using: (a) multiple forms of qualitative data (interviews, focus groups, observations); (b) multiple forms of participant perspective (service providers, service users); (c) multiple intervention sites; and (e) multiple time points (pre/post intervention). To this end we will employ a triangulation protocol, informed by the six-step process developed by Farmer et al [78]. This involves, for example, using a convergence coding matrix to summarize similarities, differences and points of 'silence' between observational, PWUO interview, and staff focus group data, including at each site and time-point. Through triangulation we will aim to understand the relative effect of each iHOST component on our primary outcomes, as well as the combined or interdependent effects of the iHOST intervention as a whole. This will take place alongside exploration of how local social contextual factors shape iHOST delivery, acceptability and impact. The primary focus of triangulation will be to identify congruence and divergence, including deviant cases for further follow-up or investigation, as well as to maximise the confidence with which judgements are made regarding potential relative intervention effects.

## MIXED METHOD SYNTHESIS

Throughout we will triangulate our qualitative data with the quantitative outcomes data to aid interpretation as well as build hypothesis regarding the likely pathways of intervention effect, which in turn will provide grounded data to inform modelling of potential future impacts under different intervention conditions. Quantitative and qualitative data collected at each phase will be analysed separately. Initial findings from each dataset will be then brought together, throughout the project, and triangulated with attention to instances of congruence, dissonance and silence. This will be informed by use of a modified triangulation protocol and convergence coding matrix [79], which – in combination with ongoing team and PPI discussion – will lead to the development of "meta-themes" [79], to provide a more holistic interpretation of intervention effectiveness and the factors critical to success or failure.

Research team meetings will provide an opportunity to critically appraise the evidence as it emerges, deliberate on key findings, resolve and explore any 'inter-method discrepancies' arising from triangulation [79] and shape the direction of the study. Summaries of the mixed method findings pertaining to each evaluation site will be discussed and refined in research team meetings to enable the building and testing of explanatory theories in relation to our outcome measures. We will, for example, be attune to the way in which qualitative interview and observational data enables capture of secular changes at intervention sites to inform before/after analysis interpretation, also to contextual site-specific factors such as discrepancies in staff recording practices of discharge against medical advice, ward absences and inpatient illicit drug use.

Our mixed method synthesis activity scheduled for months 28-33 will involve an iterative process of disseminating and further synthesising these findings, through workshops with the team, PPI and relevant stakeholders to discuss and refine our mixed-method interpretation with attention to considering the

transferability and scalability of iHOST across diverse NHS settings (with or without iHOST adaptations). We will also invite feedback through website and webinar dissemination of preliminary findings, drawing on the approach of Fulop et al. [80] who held a series of mixed media events to engage diverse range of participants to reflect on how the interpretation of mixed-method findings could inform successful system change to improve stroke outcomes, and the potential transferability of their findings to other conditions. Our final analysis and recommendations for policy, practice and service delivery will be based on the combined learning from these synthesis workshops.

## REVIEW STRATEGY

We will carry out a systematic review of peer-reviewed research that evaluates interventions aiming to improve opioid substitution therapy in acute hospital settings. The review aims to inform a template policy for opioid substitution therapy and management of opioid dependence in acute hospital settings in the UK. We will search MEDLINE, EMBASE, PsycINFO and CINAHL for articles that include the following concepts in the title and abstract fields:

**Concept 1, Acute hospital settings:** "hospital\*" OR "inpatient" OR "emergency department" OR "accident and emergency" OR "admission" OR "surg\*"

**Concept 2, Opioid agonist therapy:** "opioid agonist therapy" OR "opioid agonist treatment" OR "opiate substitution therapy" OR "methadone" OR "buprenorphine" OR "medication assisted treatment" OR "medications for addiction treatment" OR "medication for opioid use disorder"

The population included in this review are patients at acute hospitals who are dependent on opioids, including those who use illicit opioids such as heroin and those who have prescriptions of opioid agonist therapy (methadone or buprenorphine or other substitution medicines prescribed for opioid dependence). Where some study participants are eligible but others are not (e.g. the study includes both outpatients and inpatients), we will exclude studies where more than 25% of participants are not eligible, see criteria below:

### Inclusion criteria:

- (1) Participants are patients at an acute hospital, either as an inpatient or in accident & emergency / emergency department.
- (2) Study participants have a history of using illicit opioids or are prescribed opioid agonist therapy. Participants may use alcohol or other drugs in addition to opioids.

### Exclusion criteria:

- (1) Participants are outpatients.
- (2) Participants are patients at a specialist mental health hospital.
- (3) Participants have no history of using illicit opioids.
- (4) Participants are newly born babies (for example being treated for neonatal opioid withdrawal syndrome)

We will limit the review to studies published in the English language, and will not limit by date, country of study, or study type. We will include both quantitative and qualitative studies. We anticipate that the review will include various study designs, interventions, and outcomes. For example, we will include studies that compare patient outcomes associated with different opioid substitution regimes, studies that evaluate non-pharmacological approaches to improving access to opioid substitution such as peer support, and studies of the benefits associated with improved continuity of opiate substitution between community and hospital settings. Studies must compare outcomes with and without the intervention. This comparison may be quantitative or qualitative. The comparator may be defined as "treatment as usual" or alternative OAT strategies. Given the likely diversity of studies included in the review, we will not conduct a standardised risk-of-bias assessment. For each study, we will identify key limitations in the study design so that these can be summarised in analysis. We will describe the quality and results of these studies in narrative review, and we plan to use a "realist review" [81] framework to build a theory-based framework for the potential benefits of opioid substitution in acute hospitals. A "realist review" approach aims to summarise evidence on "what works for whom, in what circumstances, in what respects and how" [81]. The review protocol has been registered on PROSPERO [# CRD42022313237] and is available at this link:

[https://www.crd.york.ac.uk/prospere/display\\_record.php?ID=CRD42022313237](https://www.crd.york.ac.uk/prospere/display_record.php?ID=CRD42022313237)

